8.8.12.4. Clinical Laboratory Assessments

Blood and urine samples will be collected at the timepoints specified in [Table 4](#) for specific hematology, biochemistry and urinalysis assessments listed in [Table 5](#). Samples will be collected in accordance with the site's standard procedures and analyzed by a central laboratory. Laboratory assessments may be repeated at the investigator's discretion.

Table 5: Clinical Laboratory Assessments

Hematology	Chemistry	Urinalysis
Hematocrit	Sodium	Color
Hemoglobin	Potassium	pH
Red blood cell count	Glucose	Specific gravity
White blood cell count and differential ^a	Creatinine	Ketones
Platelets	Total protein	Protein
	Blood urea nitrogen (BUN)	Glucose
	Albumin	Bilirubin
	Total bilirubin	Nitrite
	Alanine aminotransferase (ALT)	Urobilinogen
	Aspartate aminotransferase (AST)	Occult blood
	Lactic dehydrogenase (LDH)	Microscopic examination
	Gamma-glutamyl transferase (GGT)	only if urinalysis dipstick results are abnormal
	Alkaline phosphatase (ALK-P)	
	Creatine phosphokinase (CPK)	
	Thyroid stimulating hormone (TSH) ^b	

^a White blood cell differential count (absolute values) will include basophils, eosinophils, lymphocytes, monocytes and neutrophils.

^b At screening only.

8.8.13. Randomization

At the timepoint specified in [Table 4](#), subjects will be randomized as outlined in [Section 9.4](#).

8.8.14. Drug Dispensation and Reconciliation

[Section 9](#) provides information related to drug dispensing procedures. Study drug (naltrexone, PBO-N, BUP, naloxone and VIVITROL) will be administered by clinical study staff at the timepoints specified in [Table 4](#). The clinical study site is responsible for study drug storage, handling and accountability as outlined in [Section 10](#).

8.8.15. Adverse Event Monitoring

AEs will be monitored continuously from the time a subject signs the informed consent document until the completion of the final study visit (see [Table 4](#)). AEs and SAEs are defined in [Section 12.1](#) and [12.2](#), respectively. [Section 12.4](#) provides guidance on the monitoring and recording requirements for AEs. [Section 12.5](#) provides guidance on the reporting requirements for SAEs.

8.9. Study Requirements and Restrictions

8.9.1. Prohibited Medications and Substances

The medications and substances listed below are prohibited for the specified time periods:

- Methadone is prohibited at least 30 days prior to Day -5 and for the duration of the study
- All opioid agonists (except BUP when administered during applicable study days), including opioid-containing cough medications, are prohibited for the duration of the study
- Naltrexone is prohibited for at least 90 days prior to Day -5 and for the duration of the study (except when administered during applicable study visits)
- On days when cognitive assessments are conducted (see [Table 4](#)), caffeine and nicotine (oral, inhaled or smoked) are prohibited within 30 minutes prior to the start of the assessments. A transdermal nicotine patch may remain in place. Throughout the residential period, nicotine replacement therapy is permissible in accordance with prevailing clinical policy of the residential unit.

8.9.2. Ancillary Medications

Subjects will receive ancillary medications on a standing schedule to treat symptoms of withdrawal, such as autonomic arousal, sleep disturbance, muscle tension and anxiety. Beginning on Day -2, medications listed in [Table 6](#) will be provided to subjects as a standing regimen during the residential phase of the study (see [Table 4](#)). In the event that a subject is admitted for the residential stay early (on Days -5, -4, or -3), the ancillary medication regimen will begin as soon as the subject becomes residential. If needed for AE treatment or prophylaxis, ancillary medications may be initiated at the clinician's discretion on or after Day -5. Because mild symptoms of withdrawal may be present for several days after the VIVITROL injection, subjects will continue using ancillary medications on a modified schedule (see [Table 4](#)) through Day 11 (or, for 3 days after VIVITROL injection).

Ancillary medications are commercially available and should be stored according to package insert instructions.

Table 6: Ancillary Medications

Medication	Dose Regimen	
	Days -2 to 7	Days 8/8a-11 ^a
Clonidine	0.1 mg oral tablet, 2 times a day	0.1 mg oral tablet, 1 time a day (only AM dose)
Clonazepam	0.5 mg oral tablet, 2 times a day	0.5 mg oral tablet, 1 time a day (only AM dose)
Trazodone hydrochloride	100 mg oral tablet, at bedtime	100 mg oral tablet, at bedtime

^a For subjects receiving VIVITROL on Day 8/8a, ancillary medications will be reduced on Days 9 through 11, as indicated.

Subjects will also be provided with a supply of sports hydration drink, which they will be encouraged to drink liberally.

8.9.3. Concomitant Medications

Prescribed psychoactive medications, including anxiolytics and antidepressants, will be allowed for the duration of the study provided the dose is stable at the time of the screening visit.

8.9.4. Contraception and Pregnancy

All male and female subjects must agree to use an acceptable method of contraception for the duration of the study unless they are surgically sterile or postmenopausal (see below). The following are considered acceptable methods of contraception:

- Double-barrier protection (such as a condom with spermicide or a diaphragm with spermicide)
- Intrauterine device (IUD)
- Hormonal contraceptives (such as birth control pills or patches, a vaginal ring or a contraceptive implant); oral contraceptives should be initiated at least 30 days prior to Screening

Subjects who are abstinent are eligible, provided they agree to use an acceptable contraceptive method should they become sexually active.

Subjects who are surgically sterile are exempt from the requirement to use contraception. Women who have undergone a hysterectomy, bilateral tubal ligation or bilateral salpingo-oophorectomy are considered surgically sterile. Men who have undergone a vasectomy are considered surgically sterile. Partner vasectomy is not considered an approved acceptable method of contraception for a female subject.

Women who are postmenopausal are also exempt from the requirement to use contraception. For the purpose of this study, postmenopausal is defined as the permanent cessation of menstruation for at least 12 months prior to screening in women who are 45 years of age or older.

If a subject becomes pregnant while participating in the study, she will be discontinued from study drug immediately. The early termination and safety follow-up visits will be scheduled and the pregnancy will be reported to Alkermes. Additional follow-up may be required. Pregnancies in female partners of male subjects should also be reported and will be followed in the same manner.

A Pregnancy Report Form must be submitted to Alkermes (per [Section 12.5](#)) immediately, within 24 hours of awareness of the pregnancy, irrespective of whether an AE has occurred. The pregnancy will be followed until completion or termination. If the outcome of the pregnancy meets the criteria for classification as an SAE, it should be reported following the SAE procedure (see Section 12.5).

8.10. Residential Period

Subjects will be confined to a residential unit for 9 to 11 days (Days -2 to 8/8a); the residential period may be longer for subjects who are admitted to the residential unit earlier during the BUP Lead-in Period, or for subjects who fail the naloxone challenge on Day 8/8a and remain on the residential unit per Investigator judgment.

9. TREATMENT OF SUBJECTS

9.1. Investigational Product, Dosage, Duration and Mode of Administration

Naltrexone will be supplied at the doses specified in [Table 3](#) and provided as tablets for oral administration. Naltrexone will be administered as 2 doses, given at least 1 hour apart, on Days 1 to 7.

9.2. Reference Therapy, Dosage, Duration and Mode of Administration

Placebo naltrexone (PBO-N) tablets will match the naltrexone drug product and will be administered as 2 doses, given at least 1 hour apart, on Days 1/1a to 7.

Sublingual BUP (up to 4 mg) will be administered daily to all subjects during the BUP Lead-in Period (Days -5 to -1). On Days 1/1a to 7, BUP dose will be tapered (see [Table 3](#)).

9.3. Treatment Adherence

Clinical study staff will administer study drug on an inpatient basis and record compliance for each subject in the relevant source document(s).

9.4. Randomization/Method of Assigning Subjects to Treatment

Subjects will be randomly assigned in a 1:1 ratio to 1 of 2 treatment groups: naltrexone + BUP or PBO-N + BUP, stratified according to low (<8 mg/day) vs. high (8 mg/day) BUP maintenance dose at the time of initiation of the BUP Lead-in Period. The naltrexone or PBO-N assignment will be blinded while the BUP dose will be open-label. A randomization schedule will be prepared by an independent biostatistician and uploaded into an Interactive Web Response System (IWRS). The pharmacist or designee will contact the IWRS, which will assign the subject to a treatment group according to the next available randomization record. The unblinded site pharmacist or designee will dispense naltrexone or placebo for administration to subjects.

9.5. Blinding

This is a double blind study. All Alkermes staff, clinical staff and subjects will be blinded to treatment assignment until database lock. At each study site, study medications will be prepared by an unblinded research pharmacist who has no contact with participants in the trial. The investigator is responsible for all trial-related medical decisions. If the investigator deems it necessary to break the study blind in the interest of a subject's medical safety, he or she must make every effort to contact the sponsor medical monitor before the blind is broken. If the site is unable to contact the medical monitor prior to breaking the blind, the medical monitor must be contacted within 24 hours following disclosure of study drug assignment.

Breaking the blind for a single subject will not affect the blind for the remaining subjects.

10. STUDY DRUG MATERIALS AND MANAGEMENT

10.1. Study Drug

Naltrexone for oral administration will be provided as white caplet-shaped IR tablets in the following dosages: 0.25, 0.5, 1.5, 3, 7.5 and 15 mg. Daily naltrexone doses are described in [Table 3](#) with total daily doses ranging from 0.5 to 30 mg.

Placebo to match naltrexone drug product (PBO-N) will be provided as white caplet-shaped IR tablets.

Commercially available BUP will be supplied at the doses specified in [Table 3](#) as a rapidly disintegrating tablet for sublingual administration. Buprenorphine will be administered in up to 4 mg daily dose during the lead-in (Days -5 to -1). The dose will then taper down to zero mg during the transitional dosing period leading up to the naloxone challenge (Days 1-7).

Commercially manufactured 1 mg/mL naloxone will be supplied by Alkermes as 2 mL single-dose prefilled syringes with 21 G × 1½ needles.

VIVITROL 380 mg will be supplied by Alkermes in single-use kits, each containing a 380 mg vial of VIVITROL microspheres and the diluent for suspension.

10.2. Packaging and Storage

Naltrexone tablets and placebo to match naltrexone tablets (PBO-N) will be supplied in 30-count bottles. The primary packaging consists of 60-cc high density polyethylene (HDPE) bottles heat sealed with a 1.1 g desiccant and polypropylene cap. The material should be stored at not more than 25°C.

All commercially available products are to be stored according to the manufacturer's recommendations.

Buprenorphine, a Schedule III narcotic, must be stored in accordance with US restrictions related to controlled substances.

10.3. Accountability

The clinical site is required to maintain current drug dispensation and accountability logs throughout the study as well as through IWRS. All unused supplies will be checked against the drug movement records during the study and/or at the end of the study.

Buprenorphine, a Schedule III narcotic, should be accounted for in accordance with the requirements of the Controlled Substances Act.

10.4. Handling and Disposal

Following completion and verification of accountability logs, all unused and used products must be destroyed according to applicable local and federal regulations. Alternatively, the sponsor may arrange for destruction with a third-party vendor operating in accordance with GCP and/or Good Manufacturing Practice (GMP), as applicable. Buprenorphine, as a Schedule III narcotic, should be handled and disposed of in accordance with the requirements of the Controlled Substances Act.

10.5. Management of Ancillary Medications

The ancillary medications are commercially available and should therefore be stored according to manufacturer instructions. Clonazepam is a Schedule IV controlled substance and should therefore be stored in accordance with US restrictions on controlled substances and should be accounted for, handled and disposed of in accordance with the requirements of the Controlled Substances Act.

11. ASSESSMENT OF EFFICACY

Efficacy will be assessed via the following:

- COWS score
- SOWS score
- Desire for opioids using a VAS
- PGART

Exploratory Endpoints:

The following exploratory assessments (described in detail in [Section 8.8](#)) will be conducted:

- Pupil diameter (measured during clinical testing sessions)
- QSUI
- HAM-D
- BAC Symbol Coding test
- COWA task
- WMS-III SS test
- CPT
- TAP

12. ASSESSMENT OF SAFETY

Safety and tolerability will be assessed via the following:

- AEs
- Vital signs and arterial oxygen saturation (measured during clinical testing sessions)
- Laboratory test results
- ECG parameters (uncorrected QT, QT interval corrected for heart rate using the Fridericia formula [QTcF], QT interval corrected for heart rate using the Bazett formula [QTcB], HR, RR, and QRS intervals)
- C-SSRS scores

12.1. Definition of Adverse Event

An AE is any untoward medical occurrence in a patient or clinical investigation subject administered a pharmaceutical product. The occurrence, which may or may not have a causal relationship with the investigational treatment, may include any clinical or laboratory change that does not commonly occur in that subject and is considered clinically significant.

If the severity of a subject's withdrawal symptoms necessitates administering a nonstudy medication, or doses of an ancillary medication that exceed the standing regimen, the condition being treated should be noted as an AE.

Illnesses present prior to the subject signing the informed consent form (ICF) are considered to be pre-existing conditions and are documented on the medical history eCRF. Pre-existing conditions that worsen during the study are entered on the AE eCRF.

All out-of-range laboratory values will be deemed as clinically significant or not clinically significant by the investigator. Clinically significant values will be considered AEs and recorded as such on the eCRFs.

Pregnancy is not considered an AE, although a subject will be withdrawn from the study if a pregnancy occurs. As described in [Section 8.9.4](#), the pregnancy, including a partner's pregnancy, must be reported to Alkermes, and additional follow-up may be required.

12.2. Definition of Serious Adverse Event

An SAE is any AE, occurring at any dose and regardless of causality that meets one or more of the following criteria:

- Results in death
- Is life-threatening. The subject is at immediate risk of death from the reaction as it occurs. This does not include reaction that, had it occurred in a more severe form, might have caused death
- Requires inpatient hospitalization or prolongation of existing hospitalization

- Results in persistent or significant disability/incapacity (eg, a substantial disruption of a person's ability to conduct normal life functions)
- Is a congenital anomaly/birth defect

Important medical events that may not result in death, be immediately life threatening or require hospitalization may be considered to be SAEs when, based upon appropriate medical judgment, they may jeopardize the patient or subject and may require intervention to prevent one of the other outcomes listed above.

Admission to a hospital or an inpatient unit for a non-medical reason (ie, social stay admission) during the study in the absence of untoward medical occurrence will not be considered as an SAE, but will be captured as an AE.

Hospitalization due to worsening of behavioral health-related issues should be reported as an SAE.

12.3. Relationship to Study Drug

The assessment of study drug relationship to each AE will be reported on the appropriate source document (and SAE form, in the event of an SAE) by the investigator (or designated sub-investigator) according to his/her best clinical judgment. The criteria listed in [Table 7](#) should be used to guide this assessment. Please note that not all criteria must be present to be indicative of a particular drug relationship. All study drugs are considered "test drugs" for the purposes of the definitions listed in the table.

Table 7: Adverse Event Causality Guidelines

Relationship	Criteria for assessment
Definitely related	
There is evidence of exposure to the test drug.
 
AND
 
The temporal sequence of the AE onset relative to administration of the test drug is reasonable.
 
The AE is more likely explained by the test drug than by another cause.
 
Dechallenge (if performed) is positive.
 
Rechallenge (if feasible) is positive.
 
The AE shows a pattern consistent with previous knowledge of the test drug or test drug class.

Probably related	
There is evidence of exposure to the test drug.
 
AND
 
The temporal sequence of the AE onset relative to administration of the test drug is reasonable.
 
The AE is more likely explained by the test drug than by another cause.
 
Dechallenge (if performed) is positive.

Possibly related	
There is evidence of exposure to the test drug.
 
AND
 
The temporal sequence of the AE onset relative to administration of the test drug is reasonable.
 
The AE could have been due to another equally likely cause.
 
Dechallenge (if performed) is positive.

Probably not related	
There is evidence of exposure to the test drug.
 
AND
 
There is another more likely cause of the AE.
 
Dechallenge (if performed) is negative or ambiguous.
 
Rechallenge (if performed) is negative or ambiguous.

Definitely not related	
The subject did not receive the test drug.
 
OR
 
Temporal sequence of the AE onset relative to administration of the test drug is not reasonable.
 
OR
 
There is another obvious cause of the AE.

12.4. Monitoring and Recording of Adverse Events

AE data collection will begin after a subject signs the ICF and will continue until completion of the final safety follow-up visit (Visit 10) or 28 days after the final dose of study drug. Any AE or SAE having an onset after the safety follow-up visit will not be collected or reported unless the investigator feels that the event may be related to the study drug.

Subjects will be instructed by the investigator or designee to report the occurrence of any AE. All volunteered, elicited and observed AEs are to be recorded on the AE eCRFs.

The investigator will assess all AEs regarding any causal relationship to the study drug (see [Section 12.3](#)), the intensity (severity) of the event, action taken and subject outcome.

The following criteria should be used to guide the assessment of intensity (severity):

- **Mild:** Causes awareness of sign or symptom, but is easily tolerated; does not interfere with usual activities
- **Moderate:** Causes discomfort enough to interfere with usual activities
- **Severe:** Is incapacitating; results in inability to work or perform usual activities

All AEs will be followed until resolution, until deemed stable by the investigator or until the subject is deemed by the investigator to be lost to follow-up.

For clinical study safety reporting purposes, the most recent version of the Investigator's Brochure will be used as the reference document to designate event expectedness.

Withdrawal from the study as a result of an AE and any therapeutic measures that are taken shall be at the discretion of the investigator. If a subject withdraws from the study for any reason, any ongoing AEs will be followed until resolution, until deemed stable by the investigator or until the subject is deemed by the investigator to be lost to follow-up.

12.5. Reporting of Serious Adverse Events and Pregnancy

All SAEs and pregnancies must be reported to Alkermes via ^{PPD} [REDACTED] immediately, within 24 hours of discovery, by emailing: ^{PPD} [REDACTED] or by faxing the report to the following:

FAX Number: ^{PPD} [REDACTED]

The written report for SAEs should be submitted on the SAE form provided for this purpose. The SAE report must include the Investigator's opinion as to whether the event is study drug-related. If this relationship is determined to be possibly, probably or definitely related to study drug, evidence to support this assessment must also be provided.

The written report for pregnancies in female subjects and in female partners of male subjects should be submitted on the Pregnancy Report Form provided for this purpose.

13. STATISTICS

13.1. Sample Size Considerations

The primary efficacy endpoint of the study is the proportion of subjects who receive and tolerate VIVITROL injection on Day 8/8a as demonstrated by mild (COWS ≤ 12 or SOWS ≤ 10) opioid withdrawal symptoms following VIVITROL administration.

Assuming the proportion of subjects receiving and tolerating VIVITROL administration is 90% in Group 1 and 60% in Group 2, a sample size of approximately 46 subjects per treatment group will provide at least 90% power to detect a statistically significant difference between the two treatment groups at 5% level of significance in a 2-sided test.

13.2. General Statistical Methodology

In general, summary statistics (ie, n, mean, standard deviation, median, minimum and maximum for continuous variables, and number [%] of subjects in each category for categorical variables) will be provided by treatment group for all variables.

Baseline values are defined as any nonmissing assessments prior to receiving the first dose of naltrexone or PBO-N.

Source data for the summary tables and statistical analyses will be presented as by-subject data listings.

13.2.1. Study Populations

13.2.1.1. Safety Population

The safety population is defined as all randomized subjects who receive at least 1 dose of naltrexone or PBO-N.

13.3. Demographics and Baseline Data

Demographics and baseline characteristics such as gender, age, race, weight and baseline will be summarized by treatment group for the safety population.

Medical history will be summarized for the safety population using the number of observations and percentage of subjects reporting each category.

13.4. Efficacy Analyses

Efficacy analyses will be performed using the safety population.

All statistical tests will be 2-sided with a type I error rate of 5%, unless otherwise specified.

13.4.1. Primary Efficacy Endpoint

- The proportion of subjects who receive and tolerate VIVITROL injection on Day 8/8a as demonstrated by mild (COWS ≤ 12 or SOWS ≤ 10) opioid withdrawal symptoms following VIVITROL administration

The analyses will be carried out using logistic regression with treatment as a factor.

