- Brief Assessments of Cognition (BAC) Symbol Coding test
- Controlled Oral Word Association (COWA) task
- Wechsler Memory Scale-III Spatial Span (WMS-III SS) test
- Continuous Performance Test (CPT)
- Test of Attentional Performance (TAP)

Safety:

Safety and tolerability will be assessed via the following:

- Adverse events (AEs)
- Vital signs and oxygen saturation
- Laboratory test results
- ECG parameters
- C-SSRS score

Statistical Methods:**Efficacy:**Primary Efficacy Endpoint

- The proportion of subjects who receive and tolerate VIVITROL injection on Day 8/8a as demonstrated by mild (COWS ≤ 12 or SOWS ≤ 10) opioid withdrawal symptoms following VIVITROL administration

Key Secondary Efficacy Endpoint

- Proportion of days with COWS peak score ≤ 12 during the Treatment Period prior to the VIVITROL injection (Days 1/1a-7)

Other Secondary Efficacy Endpoints

- Proportion of post-VIVITROL days (Days 9-11) in which subjects in each group demonstrate mild (COWS ≤ 12) opioid withdrawal
- Mean peak COWS scores during the Treatment Period and VIVITROL Induction and Post-VIVITROL Observation Period (Days 1/1a-11)
- Area under the curve (AUC) for COWS scores during the Treatment Period and VIVITROL Induction and Post-VIVITROL Observation Period (Days 1/1a-11)
- Mean score for “desire for opioids” VAS during the Treatment Period and VIVITROL Induction and Post-VIVITROL Observation Period (Days 1/1a-11)

Exploratory Endpoints

- Number and proportion of subjects in PGART response category at the end of the Post-VIVITROL Observation Period (Day 11)
- Change from baseline in pupil diameter following study drug administration during the Treatment Period (Days 1/1a-7)
- Change in frequency of substance use from screening to Day 36 assessed via the QSUI
- AUC for SOWS scores during the Treatment Period and VIVITROL Induction and Post-VIVITROL Observation Period (Days 1/1a-11)
- Change from baseline in standardized T scores for cognitive assessments

Efficacy Analysis: The primary efficacy endpoint will be analyzed using logistic regression with treatment as a factor.

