5.3. Rationale for Selection of Dosing Regimen

Mannelli et al. reported findings from an open-label study evaluating the use of low doses of oral naltrexone, in addition to BUP and ancillary medications, to safely transition subjects from opioid dependence to VIVITROL treatment (Mannelli et al, 2014). The regimen used in this study was based upon prior clinical experience wherein low doses of naltrexone, combined with a methadone taper, reduced the severity of withdrawal symptoms during inpatient detoxification (Mannelli et al, 2003; Mannelli et al, 2009; Mannelli et al, 2012). Subjects (N=20) were given

increasing doses of naltrexone during a 7-day outpatient period, in conjunction with 3 days of BUP. Withdrawal discomfort, craving, drug use and adverse events (AEs) were assessed daily until the administration of VIVITROL on Day 8. Adverse events were assessed weekly over the following month. Fourteen of the 20 subjects received VIVITROL, and 13 subjects completed all subsequent safety assessments. Withdrawal discomfort, craving and opioid or other drug use were significantly lower during the detoxification/induction period and after VIVITROL administration, when compared with the assessments administered at pretreatment baseline. No serious AEs (SAEs) occurred. The 7-day outpatient regimen using low doses of naltrexone, in combination with BUP, in patients with opioid use disorder prior to induction to VIVITROL was reported to be safe and well tolerated. The current study design is based on the regimen described in Mannelli's recent study ([Mannelli et al, 2014](#)).

Recruitment of a clinical population maintained at a BUP dose of ≤ 8 mg/day at study entry supports tolerability of the transition from opioid agonist maintenance, while increasing generalizability. Since BUP doses of < 8 mg/day yield $< 80\%$ μ -opioid receptor occupancy ([Greenwald et al, 2003](#)) and increase risk of relapse ([D'amore et al, 2012](#)), these doses require clinical management within the protocol (ie, BUP Lead-in phase). In light of difficulty tapering to doses below 8 mg BUP ([Ling et al, 2009](#)), this study includes 2 days of residential monitoring of BUP 4 mg/day to confirm tolerability via Clinical Opiate Withdrawal Scale (COWS)/Subjective Opiate Withdrawal Scale (SOWS) prior to randomization.

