13.4.2. Key Secondary Efficacy Endpoint

- Proportion of days with COWS peak score ≤ 12 during the Treatment Period prior to the VIVITROL injection (Days 1/1a-7)

The analysis will be carried out using a negative binomial model with treatment as a factor.

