13.4.3. Other Secondary Endpoints

- Proportion of post-VIVITROL days (Days 9-11) in which subjects in each group demonstrate mild (COWS ≤ 12) opioid withdrawal

The analyses will be carried out using a negative binomial model with treatment as a factor.

- Mean peak COWS scores during the Treatment Period and VIVITROL Induction and Post-VIVITROL Observation Period (Days 1/1a-11)
- Area under the curve (AUC) for COWS scores during the Treatment Period and VIVITROL Induction and Post-VIVITROL Observation Period (Days 1/1a-11)
- Mean score for “desire for opioids” VAS during the Treatment Period and VIVITROL Induction and Post-VIVITROL Observation Period (Days 1/1a-11)

These endpoints will be analyzed using an analysis of variance (ANOVA), with treatment as a factor.

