13.4.4. Exploratory Endpoints

- Number and proportion of subjects in PGART response category at the end of the post-VIVITROL observation period (Day 11)

The analyses will be carried out using a logistic regression model with treatment as a factor.

- Change from baseline in pupil diameter following study drug administration during the Treatment Period (Days 1/1a-7)
- Change in frequency of substance use from screening to Day 36 assessed via the QSUI
- AUC for SOWS scores during the Treatment Period and VIVITROL Induction and Post-VIVITROL Observation Period (Days 1/1a-11)
- Change from baseline in the standardized T scores for cognitive assessments

The analyses will be carried out using an analysis of covariance (ANCOVA) with treatment as a factor.

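### Randomization is stratified by BUP maintenance dose, but the primary logistic regression names treatment as its only factor; if dose is prognostic, the test is mildly conservative and loses a little power

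*Protocol*

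**What the plan says.** Section 9.4 assigns subjects 1:1, "stratified according to low (<8 mg/day) vs. high (8 mg/day) BUP maintenance dose" at the start of the lead-in period. The synopsis and section 8.1 describe the same stratification, and no other stratification factor is named.

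The primary model is written twice:
- Synopsis: "The primary efficacy endpoint will be analyzed using logistic regression with treatment as a factor".
- Section 13.4.1: "The analyses will be carried out using logistic regression with treatment as a factor".

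The later efficacy sections follow the same pattern:
- Section 13.4.2 (key secondary): "The analysis will be carried out using a negative binomial model with treatment as a factor".
- Section 13.4.3 (peak COWS, COWS AUC and desire VAS): "These endpoints will be analyzed using an analysis of variance (ANOVA), with treatment as a factor".
- Section 13.4.4 (most exploratory endpoints): "The analyses will be carried out using an analysis of covariance (ANCOVA) with treatment as a factor". An ANCOVA implies a covariate, but none is named.

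On sample size, section 13.1 assumes 90% versus 60% success and a two-sided 5% test, and says that "a sample size of approximately 46 subjects per treatment group will provide at least 90% power".

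**The concern.** Stratified randomization makes the arms nearly equal in their mix of low-dose and high-dose subjects. If the two dose groups differ in their chance of success, the true sampling variance of the treatment comparison depends only on the variation within strata. A model without the stratum estimates that variance from the pooled data, which also contain the variation between strata. Its standard error is then too large, the actual type I error falls below what it would otherwise be, and some power is given up.

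Whether entry dose predicts success is not known. Section 5.3 gives a qualitative hint ("In light of difficulty tapering to doses below 8 mg BUP"). Against that, section 8.2.2 has all subjects stabilized on 4 mg or less for 5 days before randomization, which may weaken any link. What is at stake is therefore efficiency, and only if dose matters.

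**Working it through.** **Inputs from the protocol.** 46 per arm; 90% versus 60%; two-sided 5% (sections 13.1 and 13.4); 1:1 allocation within two dose strata (section 9.4).

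**Assumptions, because the protocol gives no figures.** Stratum odds ratio (low versus high dose, same in both arms) of 1, 2, 3 or 5; equal strata unless stated; dose exactly balanced between arms. Stratum rates are set so that each arm keeps its overall rate. For example, odds ratio 5 gives 96.3%/83.7% for an arm at 90% and 78.2%/41.8% for an arm at 60%.

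**Step 1: the plan's own figure.** The usual two-proportion formula gives

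z = (|p1 − p2|·√n − 1.96·√(2·p̄·(1 − p̄))) / √(p1(1 − p1) + p2(1 − p2))

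= (0.30 × 6.782 − 1.96 × √0.375) / √0.33 = (2.035 − 1.200) / 0.574 = 1.45,

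so power is 92.7%. Exact enumeration of the treatment-only logistic Wald test gives 92.5%. The claim of at least 90% reproduces.

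**Step 2: why the test becomes conservative.** Take a null success rate of 75%. The pooled variance per subject is 0.75 × 0.25 = 0.1875.

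- Odds ratio 2 gives stratum rates of 0.814 and 0.686. The mean within-stratum variance is (0.814 × 0.186 + 0.686 × 0.314)/2 = 0.1834. The true standard error is √(0.1834/0.1875) = 0.989 of the one used. The effective critical value is 1.96/0.989 = 1.98, so the approximate type I error is 4.75%.
- Odds ratio 5 gives rates of 0.888 and 0.612. The mean within-stratum variance is 0.168, the ratio √(0.168/0.1875) is about 0.948, and the critical value is about 2.07. The approximate type I error is 3.9%.

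**Step 3: exact figures.** All outcome tables for 46 per arm in two strata were enumerated, and both logistic models were fitted to each (two-sided Wald, 5%). Tables with an arm at 0% or 100% success count as non-significant.

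| Stratum odds ratio | 1 | 2 | 3 | 5 |
|---|---|---|---|---|
| Type I error at 75%, treatment only | 4.8% | 4.5% | 4.2% | 3.7% |
| Type I error at 60%, treatment only | 4.63% | 4.31% | 3.88% | 3.15% |
| Power 90% vs 60%, treatment only → with stratum | 92.5 → 92.5 | 92.7 → 92.9 | 93.0 → 93.5 | 93.5 → 94.6 |
| Power 85% vs 60% | 78.0 → 78.1 | 78.2 → 78.7 | 78.6 → 79.8 | 79.2 → 82.0 |
| Power 80% vs 60% | 56.0 → 56.2 | 56.1 → 56.9 | 56.2 → 58.0 | 56.4 → 60.4 |

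With the stratum in the model, type I error is 4.7–4.8% at 75% success and 4.7–5.0% at 60%.

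**Step 4: sensitivity.** With 14 or 32 of the 46 per arm in the 8 mg stratum and odds ratio 5, treatment-only type I error at 75% is 3.5% or 4.1%. The power gain from adding the stratum is at most about 1 point at 90% versus 60%, and 3.9 or 2.2 points at 80% versus 60%. A separate run took the odds ratio to 8 with high-dose shares of 30% to 70%. Treatment-only type I error was 2.8–3.8%, and the gain at the planned rates was 0.9 to 1.6 points. Nothing in the protocol supports so strong an association.

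**The case against.** The strongest reply is that the protocol's wording is shorthand. It says treatment is a factor, not the sole factor, and its ANCOVA names no covariate, so full model terms may be left to the SAP. That is fair as far as it goes: an SAP, not available here, may add the stratum. But the protocol does not leave the primary model open. It states one, twice, without the stratum. If the SAP differs, the same phrase would bring the two documents into line.

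Second, an unadjusted comparison after stratified randomization is valid, and the premise that dose is prognostic is unproven. Section 8.2.2 also requires a COWS score of 12 or lower before randomization, which screens out subjects who do not tolerate the reduced dose. All of this stands and is why the point is minor. The 4-point loss needs both an odds ratio of 5 and an effect smaller than planned.

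Third, section 13.4.1 does not specify the Wald test. With a likelihood-ratio test at 75% success, treatment-only type I error is 5.5, 5.2, 4.8 and 4.3% at odds ratios 1, 2, 3 and 5, against about 5.2–5.5% with the stratum. So the statement that the test runs below 5% depends on the test chosen at weak stratum effects, and part of the Wald shortfall (4.8% at odds ratio 1) is unrelated to stratification. The choice of test also matters more at the planned rates: with no stratum effect, likelihood-ratio power is 94.1% against 92.5% for Wald. The decline as dose becomes more prognostic is the same for both tests.

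Fourth, no figures were computed for the models in 13.4.2 to 13.4.4, and adding the stratum changes the treatment odds ratio from an overall to a within-stratum one. Both remarks are correct. The extension rests on consistency with the design, not on a calculated gain.

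**Conclusion.** The point holds, as an optional improvement. The stated primary model omits the only factor on which randomization is stratified. If dose is prognostic, the cost is a conservative test and, over odds ratios 1 to 5, a power loss of 0 to about 1 point at the planned rates and up to 4 points at 80% versus 60%. If dose is not prognostic, the two models perform almost identically (92.5% power either way). Type I error is not inflated, and the claim of at least 90% power is unaffected. The sizes rest on assumed stratum odds ratios and shares, on exact balance of dose between arms and, for the tabulated levels, on the Wald test. Confidence in the practical benefit is moderate because the protocol does not say how strongly entry dose predicts outcome.

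**What to change.** In the synopsis and section 13.4.1, specify logistic regression with treatment and randomization stratum (BUP maintenance dose <8 vs 8 mg/day) as factors. Add the stratum in the same way to the models in 13.4.2, 13.4.3 and 13.4.4. Because the adjusted odds ratio is a within-stratum quantity, keep reporting the overall success proportion in each arm beside it, so that the result can still be read against the 90% and 60% in section 13.1.

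The cost is one phrase in each place. The stratum is already recorded for randomization, and neither sample size nor conduct changes. Making the change before unblinding also prevents a later dispute over which analysis is primary.
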